7.2.5 Pharmacodynamics Analysis Set (PDAS)

The biomarker pharmacodynamics analysis set (PDAS) will include the subjects from the SAF population for whom sufficient pharmacodynamic measurements were collected. The PDAS will be used for all analyses of pharmacodynamics data.

7.3 Demographics and Other Baseline Characteristics

Demographics and other baseline characteristics will be summarized by treatment group for the SAF. Descriptive statistics will include number of subjects, mean, standard deviation, minimum, median and maximum for continuous endpoints, and frequency and percentage for categorical endpoints.

7.4 Analysis of Efficacy

Efficacy analysis will be conducted on the FAS and PPS. The interpretation of results from statistical tests will be based on the FAS. The PPS will be used to assess the robustness of the results from the statistical tests based on the FAS. All randomized subjects will be analyzed according to the treatment to which they are randomized.

7.4.1 Analysis of Primary Endpoint

7.4.1.1 Primary Analysis

The primary endpoint is PFS assessed by the blinded IRR. For each subject, PFS is defined as the time from the date of randomization until the date of radiological disease progression (i.e., PFS#1) assessed by IRR, or until death due to any cause. If a subject has neither progressed nor died, the subject will be censored at the date of last radiological assessment. Subjects who receive any further anticancer therapy for the disease before radiological progression will be censored at the date of the last radiological assessment before the anticancer therapy started. If progression or death occurs after missing 2 scheduled radiological assessments, the subject will be censored at the date of last radiological assessment or at the date of randomization if no postbaseline radiological assessment is available.

The primary analysis will be performed when approximately 420 PFS#1 events have been observed.

The distribution of PFS will be estimated for each treatment arm using Kaplan-Meier methodology and compared between Arm A and Arm B using log-rank test stratified by ECOG PS (0 and 1 combined versus 2), EGFR mutation type, and TKI chosen (erlotinib versus gefitinib). In addition, stratified Cox proportional hazard model will be used to estimate the hazard ratio and the corresponding 95% confidence interval.

The primary analysis will be performed using the FAS.

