4.5 Assignment and Allocation

Randomization in a 1:1 ratio to each of the 2 treatment arms will be performed via Interactive Response Technology (IRT). Randomization will be stratified by ECOG PS (0, 1 or 2), EGFR mutation type (exon 19 deletion or mutation in exon 21 L858R), TKI chosen (erlotinib versus gefitinib) and race (Asian versus nonAsian). At the beginning of the trial, prior to site initiation and shipment of study drug supplies, each investigator will select either erlotinib or gefitinib to be utilized for all patients randomized to the comparator arm at their site. Prior to

the initiation of the study treatment, the site staff will contact the IRT in order to determine the randomly assigned treatment arm. Specific procedures for randomization through the IRT are contained in the study procedures manual.

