7.4.2 Analysis of Secondary Endpoints

7.4.2.1 Overall survival

OS is defined as the time from the date of randomization until the documented date of death from any cause. All events of death will be included, regardless of whether the event occurred while the subject is still taking study drug or after the subject discontinues study drug. Subjects who are still alive at the time of analysis will be censored at the last day known to be alive.

The distribution of OS will be estimated for each treatment arm using Kaplan-Meier methodology and compared between Arm A and Arm B using the log-rank test stratified by ECOG PS (0 and 1 combined versus 2), EGFR mutation type (exon 19 deletion or mutations in exon 21 [L858R]) and TKI chosen (erlotinib versus gefitinib). In addition, stratified Cox

proportional hazard model will be used to estimate the hazard ratio and the corresponding 95% confidence interval.

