7.4.2.4 Disease Control Rate (DCR)

The DCR is defined as the proportion of subjects with a complete or partial objective response or a stable disease based on RECIST V1.1.

The comparison of DCR between Arm A and Arm B will be performed using CMH test stratified by ECOG PS (0 and 1 combined versus 2), EGFR mutation type (exon 19 deletion or mutations in exon 21 [L858R]) and TKI chosen (erlotinib versus gefitinib). In addition, DCR for each arm will be estimated and corresponding 95% confidence interval will be constructed.

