7.4.1 Analysis of Primary Endpoint

The primary analysis will be performed on progression-free survival as assed by the IRR (PFS#1) on the FAS. In order to compare the PFS#1 between ASP8273 and the comparator Erlotinib/Gefitinib, the null hypothesis will be constructed:

• H₀₁: PFS of ASP8273 is not better than the comparator erlotinib/gefitinib

The accompanying alternative hypothesis is:

• H₁₁: PFS of ASP8273 is better than the comparator erlotinib/gefitinib

The primary analysis will be performed when approximately 362 PFS#1 events have been observed. Comparison of ASP8273 and erlotinib/gefitinib will be tested at 1-sided significance level of 0.025.

The distribution of PFS will be estimated for each treatment arm using Kaplan-Meier methodology and compared between Arm A and Arm B using log-rank test stratified by ECOG PS (0 and 1 combined versus 2), EGFR mutation type (exon 19 vs exon 21), and TKI chosen (erlotinib versus gefitinib). In addition, stratified Cox proportional hazard model will be used to estimate the hazard ratio and the corresponding 95% confidence interval.

The sensitivity analyses for PFS include:

- The primary analysis repeated for PPS
- The primary analysis including clinical progression as an event may be performed on the FAS
- If there is a difference in the stratification values between IRT and the CRF, primary analysis may be repeated on the FAS using CRF stratification values

Sponsor: Astellas Pharma Global Development, Inc.

ISN/Protocol 8273-CL-0302

• PFS#1 as assessed by the IRR will be analyzed using restricted mean survival time (RMST) approach from time 0 to 36 months. The restricted mean is a measure of average survival from time 0 to a specified timepoint. This approach does not require any model assumptions such as proportional hazards.

Table 4 PFS#1 Definition

Situation	Date of Event or Censor	Outcome			
No evaluable post-baseline imaging assessments, no death	Date of randomization	Censor			
Subject did not receive new anti-cancer therapy:					
Radiographical progression documented per RECIST v1.1	Date of radiological PD	Event			
No radiographical progression, but death recorded on eCRF	Date of death	Event			
No radiographical progression nor death	Date of last radiological assessment or at the date of randomization if no post-baseline radiological assessment is available	Censor			
Subject received new anti-cancer (ACT)	therapy:				

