7.8 Subgroups of Interest

PFS#1 by IRR, OS, DOR and ORR by IRR will be summarized for the subgroups defined on the basis of the categorized variables listed below:

Grouping variable Subgroups
Age group < 65 years

>=65 years - <75 years

>=75 years

Sex Female

Male

Race Asian

Non-Asian

ECOG status at baseline 0 and 1

2

EGFR status Exon 19 Deletion

Exon 21 L858R

TKI chosen Erlotinib

Gefitinib

Additional analyses may be performed to explore treatment outcome between ECOG status at baseline scores 0 and 1. Forest plots for PFS#1 by IRR and OS will be produced to summarized the treatment effect across subgroups. PFS#1 by IRR, OS, DOR and ORR by IRR may also be summarized using three treatment arms (i.e. ASP8273, Erlotinib and Gefitinib).

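### The efficacy analyses combine ECOG 0 and 1, which randomization keeps apart, with no stated reason and no sensitivity analysis at the randomized levels; the test stays valid and the cost is small

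*Protocol*

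**What the plan says.** Protocol 4.5 sets the allocation factors: "Randomization will be stratified by ECOG PS (0, 1 or 2), EGFR mutation type", together with "TKI chosen (erlotinib versus gefitinib) and race (Asian versus nonAsian"). Protocol 7.1 and SAP 3.3 and 4 repeat this.

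The analyses use coarser ECOG groups.

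- **Primary PFS.** Protocol 7.4.1.1 plans a "log-rank test stratified by ECOG PS (0 and 1 combined versus 2), EGFR mutation type, and TKI chosen (erlotinib versus gefitinib"), and SAP 7.4.1 agrees: "stratified by ECOG PS (0 and 1 combined versus 2), EGFR mutation type (exon 19 vs exon 21"), again with the TKI chosen. The stratified Cox model accompanies this test.
- **OS.** Protocol 7.4.2.1 plans a "log-rank test stratified by ECOG PS (0 and 1 combined versus 2"), plus mutation type and TKI. SAP 7.4.1.1 says the same.
- **DOR and DCR.** Protocol 7.4.2.5 and 7.4.2.4 use the same grouping; the DCR test is "stratified by ECOG PS (0 and 1 combined versus 2").
- **ORR.** Protocol 7.4.2.2 and SAP 7.4.1.2 specify a stratified CMH test without naming strata. The protocol synopsis says ORR and DCR use the time-to-event factors.
- **Investigator PFS and PFS#2** refer back to the primary test.

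No reason is given for combining 0 and 1. The only sensitivity analysis on stratification swaps IRT for CRF values (SAP 7.4.1 and 7.4.1.1). SAP 7.8 adds an optional exploration: "Additional analyses may be performed to explore treatment outcome between ECOG status at baseline scores 0 and 1".

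**The concern.** A stratified analysis normally conditions on the factors that were balanced by design. Here a split judged worth balancing at randomization is dropped from the test, from the hazard ratio and from every sensitivity analysis.

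Merging strata is usually defended by sparsity. ECOG 2 is the level most likely to be small, and it is left alone; the merger joins the two levels likely to be large.

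If patients with ECOG 0 and 1 differ in prognosis, each pooled stratum mixes two baseline hazards. The conditional hazard ratio is then pulled toward 1 and the log-rank test loses a little efficiency. OS and ORR, which are tested formally under the Hochberg procedure, carry the same grouping.

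**Working it through.** **1. The plan's own figure.** Inputs from Protocol 7.1: 420 events, HR 0.667, 1:1 allocation, one-sided alpha 0.025. Schoenfeld's formula gives power = Φ(√(420/4) × |ln 0.667| − 1.960) = Φ(10.247 × 0.4050 − 1.960) = Φ(2.190) = 98.6%, against the stated 98.7%. It reproduces.

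**2. Number of strata.**
- Randomization: 3 ECOG × 2 mutation × 2 TKI × 2 race = 24 cells.
- Planned analysis: 2 × 2 × 2 = 8 strata, on average 420/8 = 52.5 events each.
- Three ECOG levels, still without race: 3 × 2 × 2 = 12 strata, on average 420/12 = 35 events each.

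**3. Does the merger relieve thin strata?** The documents give no case mix. Assumed: ECOG 2 at 5–10%, ECOG 0 at 20–45%, exon 21 at 45%, erlotinib at 30–50%, events in proportion to patients. Expected events in a cell = 420 × ECOG share × mutation share × TKI share.
- Smallest ECOG 2 cell: from 420 × 0.05 × 0.45 × 0.30 = 2.8 to 420 × 0.10 × 0.45 × 0.50 = 9.5.
- Smallest ECOG 0 or 1 cell when kept separate: from 420 × 0.20 × 0.45 × 0.30 = 11.3 to 420 × 0.45 × 0.45 × 0.50 = 42.5.
- Cells with fewer than 10 expected events: 2 to 4, the same count with 8 or 12 strata.

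Across these mixes the thin cells are all ECOG 2 cells, and combining 0 with 1 leaves them unchanged.

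**4. Effect on power and the hazard ratio.** Stratified log-rank simulation on PFS: 600 patients, 420 events, blocks of 4 within the 24 cells, 2,500 runs per row, both tests run on the same data. Assumed: ECOG 35/57/8%, exon 21 45%, erlotinib 40%, Asian 50%, uniform accrual over 24 months, ECOG 2-versus-0 hazard ratios of 1.0, 2.0, 2.5 and 3.0 alongside the four ECOG 1-versus-0 values. The hazard ratio is the one-step estimate exp((O−E)/V).

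| True HR | ECOG 1 vs 0 HR | Power, 0/1 combined | Power, three levels | HR, combined | HR, three levels |
|---|---|---|---|---|---|
| 0.667 | 1.0 | 98.1% | 98.1% | 0.667 | 0.667 |
| 0.667 | 1.3 | 98.5% | 98.3% | 0.666 | 0.664 |
| 0.667 | 1.5 | 97.9% | 97.9% | 0.671 | 0.666 |
| 0.667 | 2.0 | 98.0% | 98.5% | 0.677 | 0.664 |
| 0.75 | 1.0 | 83.8% | 83.4% | 0.747 | 0.747 |
| 0.75 | 1.3 | 81.5% | 81.7% | 0.751 | 0.750 |
| 0.75 | 1.5 | 81.0% | 81.4% | 0.755 | 0.751 |
| 0.75 | 2.0 | 80.5% | 82.9% | 0.760 | 0.749 |

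The Monte Carlo standard error of each power is about 0.3 points at HR 0.667 and 0.8 points at 0.75. Because the two tests share data, their difference is more precise than either figure alone.

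A larger run (6,000 per scenario, same ECOG mix) at a true HR of 0.75 put three levels minus combined at −0.5, 0.0, +1.4 and +2.3 points for ECOG 1-versus-0 hazard ratios of 1.0, 1.3, 1.6 and 2.0. At 2.0 the estimates were 0.759 combined and 0.749 with three levels, a gap of 0.010.

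**5. Type I error.** Under no treatment effect the combined test rejected in 1.7% to 2.7% of runs (standard error 0.3 points), against a nominal 2.5%. There is no inflation.

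**The case against.** The strongest case for leaving the plan alone is that the grouping is pre-specified, identical in both documents, matches the subgroup split in SAP 7.8, and gives a valid test. Coarser analysis strata are an ordinary choice. All of that stands.

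Other parts also stand:

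- If ECOG 0 versus 1 carries no prognostic information, the combined test is marginally better (mean Z 4.07 versus 4.05 at HR 0.667).
- Pooling removes 4 of 12 strata. If ECOG 0 turned out to be rare, it would remove thin cells too. The documents give no ECOG mix, so this cannot be settled from them.
- Only PFS in the full analysis set was simulated. DOR covers responders only, OS is analysed at the PFS cut-off with an unstated number of deaths, and subgroups are smaller. Twelve strata could be thin there, which is why the fix needs a pooling rule.
- Three ECOG levels still do not reproduce the randomization strata, because race is also absent from the analysis.
- The three-level estimates in the table fall slightly below the true HR in places. They are one-step estimates, not the planned Cox estimates, so the gap between the two columns is the useful quantity.

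A reader might go further and infer that the documents contradict each other, that the pooled test is invalid, that pooling achieves nothing, that changing it is free, or that SAP 7.8 anticipates different outcomes in ECOG 0 and 1. None of these is supported. The two documents agree on the grouping, type I error is not inflated, and there is a small price if 0 versus 1 is not prognostic. SAP 7.8 only permits an exploratory look.

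**Conclusion.** The point holds as a minor improvement. Randomization separates ECOG 0 from 1, the efficacy analyses combine them without a reason, and no planned analysis shows whether this matters. The primary test is valid as written.

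The size depends on assumptions that the documents do not supply. With an ECOG 1-versus-0 hazard ratio of about 1.5 to 1.6, pooling moves the PFS hazard ratio toward 1 by about 0.005; at 2.0, by about 0.01. The power loss is at most about 0.5 points at the design HR of 0.667. At a true HR of 0.75 it is about 0 to 2.3 points for ECOG hazard ratios from 1.3 to 2.0. That ECOG 0 versus 1 is prognostic at all is an inference from its use as a stratification factor; no figure in the documents establishes it. The statement that pooling does not help the sparse cells rests on the assumed mixes. The effect on OS and ORR was not quantified.

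**What to change.** In Protocol 7.4.1.1, 7.4.2.1 and 7.4.2.2, and SAP 7.4.1, 7.4.1.1 and 7.4.1.2:

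1. Stratify the primary PFS analysis and the OS and ORR tests by ECOG 0, 1 and 2 as randomized, and name the strata for the ORR test.
2. Pre-specify a rule for pooling strata below a stated event count (responder count for ORR), counted over both arms together, with the order of merging fixed in advance. DOR, OS with few deaths and subgroup analyses need it.
3. Keep the current version, with 0 and 1 combined, as a sensitivity analysis beside the IRT/CRF one.

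If the sponsor prefers the combined strata as primary, the minimum is to state the reason and add the three-level analysis as a sensitivity analysis.

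The cost is wording in both documents, with no change to sample size or data collection. SAP section 1 allows revisions before database hard lock; this one should be settled before any comparative efficacy result is seen. The statistical price is 12 strata instead of 8, and about 0.5 points of power at a true HR of 0.75 if ECOG 0 versus 1 is not prognostic.

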7.4.1.2 Secondary Analysis

The same analysis of the primary endpoint as described in [Section 7.4.1.1] will be conducted using the PPS.

7.4.1.3 Subgroup Analysis

The analysis described in [Section 7.4.1.1] will be conducted in the subgroups using the FAS. Forest plot will be presented to illustrate the strength of treatment effects across subgroups defined by baseline factors.

7.4.2 Analysis of Secondary Endpoints

7.4.2.1 Overall survival

OS is defined as the time from the date of randomization until the documented date of death from any cause. All events of death will be included, regardless of whether the event occurred while the subject is still taking study drug or after the subject discontinues study drug. Subjects who are still alive at the time of analysis will be censored at the last day known to be alive.

The distribution of OS will be estimated for each treatment arm using Kaplan-Meier methodology and compared between Arm A and Arm B using the log-rank test stratified by ECOG PS (0 and 1 combined versus 2), EGFR mutation type (exon 19 deletion or mutations in exon 21 [L858R]) and TKI chosen (erlotinib versus gefitinib). In addition, stratified Cox

proportional hazard model will be used to estimate the hazard ratio and the corresponding 95% confidence interval.

7.4.2.2 Best overall response rate (ORR)

Best overall response is determined once all tumor response data for the subject is available. Subjects will be classified by best response on study as outlined in RECIST V1.1 criteria. For best overall response of SD, SD must be documented as present at least once after study entry and at least 7 weeks after first dose.

The ORR is defined as the proportion of subjects with a complete or partial objective response based on the RECIST V1.1.

The ORR (confirmed) is defined as the proportion of subjects with a confirmed complete or partial objective response based on the RECIST V1.1 in Table 3 of [Appendix 12.9].

The comparison of ORR between Arm A and Arm B will be performed using stratified CMH test. In addition, ORR for each arm will be estimated and corresponding 95% confidence interval will be constructed.

The comparison of ORR (confirmed) between Arm A and Arm B will be performed using stratified CMH test. In addition, ORR for each arm will be estimated and corresponding 95% confidence interval will be constructed. This will be a sensitivity analysis.

Hochberg procedure will be used to control the overall error rate at 1-sided 0.025 level for the secondary efficacy endpoints (OS and ORR). Only when the primary endpoint significantly favors the ASP8273 arm will secondary endpoints be tested.

7.4.2.3 PFS by the Investigator

For each subject, PFS is defined as the time from the date of randomization until the date of radiological disease progression assessed by the investigator, or until death due to any cause. If a subject has neither progressed nor died, the subject will be censored at the date of last radiological assessment. Subjects who receive any further anticancer therapy for the disease before radiological progression will be censored at the date of the last radiological assessment before the anticancer therapy started. If progression or death occurs after missing 2 consecutive scheduled radiological assessments, the subject will be censored at the date of last radiological assessment or at the date of randomization if no postbaseline radiological assessment is available.

The distribution of PFS will be estimated for each treatment arm using Kaplan-Meier methodology and compared between Arm A and Arm B using stratified log-rank test as specified in [Section 7.4.1.1]. In addition, stratified Cox proportional hazard model will be used to estimate the hazard ratio and the corresponding 95% confidence interval.

7.4.2.4 Disease Control Rate (DCR)

The DCR is defined as the proportion of subjects with a complete or partial objective response or a stable disease based on RECIST V1.1.

The comparison of DCR between Arm A and Arm B will be performed using CMH test stratified by ECOG PS (0 and 1 combined versus 2), EGFR mutation type (exon 19 deletion or mutations in exon 21 [L858R]) and TKI chosen (erlotinib versus gefitinib). In addition, DCR for each arm will be estimated and corresponding 95% confidence interval will be constructed.

7.4.2.5 Duration of Response (DOR)

DOR is defined as the time from the date of the first response CR/PR (whichever is first recorded) as assessed by IRR to the date of radiographic progression or date of censoring. If a subject has not progressed, the subject will be censored at the date of last radiological assessment or at the date of first CR/PR if no post-baseline radiological assessment is available.

The distribution of DOR will be estimated for each treatment arm using Kaplan-Meier methodology and compared between Arm A and Arm B using the log-rank test stratified by ECOG PS (0 and 1 combined versus 2), EGFR mutation type (exon 19 deletion or mutations in exon 21 [L858R]) and TKI chosen (erlotinib versus gefitinib). In addition, stratified Cox proportional hazard model will be used to estimate the hazard ratio and the corresponding 95% confidence interval.

7.4.2.6 QoL and PRO Parameters

Descriptive QoL and PRO analyses will be performed on the FAS. Completion rate for each questionnaire will be summarized. Additional analyses will be discussed in details in the statistical analysis plan.

7.4.3 Analysis of Exploratory Endpoints

7.4.3.1 PFS on Next-Line Therapy (PFS#2)

PFS#2 is defined as the time from initiation of new systemic anti-cancer treatment (excluding local radiation, surgical removal of metastatic site or protocol defined Erlotinib or Gefitinib or ASP8273 based on initial treatment allocation per subject) to investigator-determined progression, discontinuation of new treatment, start of a different treatment or death from any cause, whichever comes first. Otherwise, subjects will be censored.

Subjects who have not started new systemic anti-cancer treatment will be censored at Day 1. Subjects who are alive, started new systemic anti-cancer treatment and for whom a PFS#2 event has not been observed should be censored at the last time known to be alive.

The distribution of PFS#2 will be estimated for each treatment arm using Kaplan-Meier methodology and compared between Arm A and Arm B using stratified log-rank test as specified in [Section [7.4.1.1](#)]. In addition, stratified Cox proportional hazard model will be used to estimate the hazard ratio and the corresponding 95% confidence interval.

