- Subject misses 2 consecutive scheduled tumor assessments
- Death
- Sponsor ends long-term follow-up collection period

The subject will be discontinued from the survival follow-up period if any of the following occur:

- Subject declines further study participation (i.e., withdraws consent)
- Subject is lost to follow-up despite reasonable efforts by the investigator to locate the subject
- Death
- Sponsor ends survival follow-up period

Concomitant Medication Restrictions or Requirements:

Arm A (ASP8273)

The following medications/food are likely to influence evaluation of the safety, pharmacokinetics, or efficacy of ASP8273, and will be strictly prohibited:

- Chemotherapy, radiotherapy, immunotherapy, or other medications intended for antitumor activity
- Investigational products or therapy other than ASP8273
- Potent inhibitors (e.g., ketoconazole, grapefruit or grapefruit juice) or inducers (e.g., rifampin, phenytoin or St. John's wort) of CYP3A4
- CYP3A4 and/or P-gp substrates with a narrow therapeutic index

The use of the following medications should be avoided or used with caution and close monitoring:

- Moderate/weak inhibitors or inducers of CYP3A4
- Inhibitors or inducers of P-gp
- CYP3A4 and/or P-gp substrates

Arm B (Erlotinib/Gefitinib)

The following medications/food are likely to influence evaluation of the safety, pharmacokinetics, or efficacy of erlotinib/gefitinib, and will be strictly prohibited:

- Chemotherapy, radiotherapy, immunotherapy, or other medications intended for antitumor activity other than erlotinib/gefitinib
- Investigational products or therapy
- Potent inhibitors (e.g., ketoconazole, grapefruit or grapefruit juice) or inducers (e.g., rifampin, phenytoin or St. John's wort) of CYP3A4
- Proton pump inhibitors or drugs that cause significant elevation in gastric pH

The use of the following medications should be avoided or used with caution and close monitoring while the subject is receiving erlotinib/gefitinib:

- Moderate/weak inhibitors or inducers of CYP3A4
- Inhibitors or inducers of P-gp
- Warfarin
- For subjects who are randomized to erlotinib:
 - Potent inhibitors of CYP1A2
- For subjects who are randomized to gefitinib:
 - Potent inhibitors of CYP2D6
 - CYP2D6 substrates with narrow therapeutic index

Duration of Treatment:

Subjects will be allowed to receive ASP8273 or erlotinib/gefitinib until discontinuation criteria are met.

Endpoints for Evaluation:

Primary

- PFS as assessed by IRR

Secondary

- OS

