- ¹ If a subject discontinues study drug prior to radiographic disease progression (i.e., PFS#1), the subject should continue to undergo imaging assessment (including brain imaging when indicated and collection of tumor measurements) every 56 days (±7 days) in the posttreatment follow-up period until PFS#1 is documented per the investigator, the subject misses 2 or more consecutive scheduled tumor assessments, or the subject starts another cancer treatment, whichever occurs earlier.
- ² After PFS#1, subjects will be followed in the long-term follow-up period per institutional guidelines, but not less frequently than every 3 months to confirm survival status and collect subsequent anticancer treatment details and progression status until PFS#2 is documented or the subject starts another cancer treatment, whichever occurs earlier. Phone contact with subject is sufficient for follow-up. Additional follow-up contacts may be required per sponsor request for analysis purposes.
- ³ Quality of life (EQ-5D-5L only) will be assessed at each of the posttreatment or long-term follow-up survival contacts for 6 months after treatment discontinuation. QoL may be assessed by telephone module if follow-up contact is done by phone.
- ⁴ Subjects will be followed via phone call in the survival follow-up period approximately every 3 months to collect survival status until subject death or study closure. Additional follow-up contacts may be required per sponsor request for analysis purposes.

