Imaging will be evaluated at baseline and every 56 days (± 7 days) throughout the study. Imaging of the brain is required at baseline for all subjects, and may be repeated throughout the study as clinically indicated. If a brain lesion not previously irradiated is selected as a target lesion at baseline, the assessment should be repeated at all subsequent imaging timepoints. A blinded independent central reader will review all imaging scans to confirm complete response (CR), partial response (PR), stable disease (SD) or progressive disease (PD) per Response Evaluation Criteria in Solid Tumors (RECIST) V1.1. Disease progression

on study drug (PFS#1) should be confirmed by the blinded independent central reader before subjects are discontinued from treatment.

Following discontinuation from study drug, subjects will have a follow-up visit 30 days (+7 days) after their last dose of drug for safety assessments. If a subject discontinues study drug prior to radiographic disease progression (i.e., PFS#1), the subject should enter the posttreatment follow-up period and continue to undergo imaging assessments every 56 days (+/- 7 days) until PFS#1 is documented or the subject starts another anticancer treatment, whichever occurs earlier.

Following PFS#1, subjects will enter the long-term follow-up period and be followed every 3 months from the date of the follow-up visit for survival status and progression status on subsequent therapy (i.e., PFS#2). Subjects will be followed until PFS#2 is documented or the subject starts another anticancer treatment, whichever occurs earlier. All subsequent anticancer therapy including date and site of progression for PFS#2 will be recorded on the case report form.

Following PFS#2, subjects will enter the survival follow-up period and be followed every 3 months for survival status.

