7.4.2 Analysis of Exploratory Endpoint

7.4.2.1 PFS#2

The distribution of PFS#2 will be estimated on the FAS for each treatment arm using Kaplan-Meier methodology and compared between Arm A and Arm B using stratified log-rank test as specified in [Section 7.4.1]. In addition, stratified Cox proportional hazard model will be used to estimate the hazard ratio and the corresponding 95% confidence interval.

Table 7 PFS#2 Definition

Situation	Date of Event or Censor	Outcome
Subject did not receive new anti-cancer	Day 1	Censor
therapy		
Subject received new anti-cancer therapy:		
Subject has investigator-determined	Minimum of [Date of	Event
progression on that treatment or ended that	investigator determined PD, date	
treatment or started another therapy or death	of death, new ACT end date, or	
	start date of another therapy]	
Subject did not die nor progressed nor	Last known alive date	Censor
stopped the new ACT nor started another		
therapy at the time of analysis cutoff date		

PFS#2 = Date of Event or Censor – Date of initiation of new systemic anti-cancer treatment +1

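### PFS#2 is censored at the last date known alive, not the last date known progression-free, so time without progression follow-up counts as progression-free

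*Protocol*

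**What the plan says.** Protocol 7.4.3.1 counts as a PFS#2 event "investigator-determined progression, discontinuation of new treatment, start of a different treatment or death from any cause, whichever comes first". Subjects who are alive, have started a new systemic treatment and "for whom a PFS#2 event has not been observed should be censored at the last time known to be alive". SAP 6.1.3.1 has the same sentence, and SAP Table 7 gives the censoring date as "Last known alive date". None of the three requires the subject to have been known progression-free on that date.

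The primary endpoint is handled differently. Protocol 7.4.1.1: "If a subject has neither progressed nor died, the subject will be censored at the date of last radiological assessment". Investigator PFS (7.4.2.3) and duration of response (7.4.2.5) also use the last radiological assessment.

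On data collection, Protocol Table 2, footnote 2, has long-term follow-up contacts at least every 3 months "to confirm survival status and collect subsequent anticancer treatment details and progression status until PFS#2 is documented", and adds: "Phone contact with subject is sufficient for follow-up". Protocol 2.2.1 then states: "Following PFS#2, subjects will enter the survival follow-up period and be followed every 3 months for survival status". In Table 2 the survival period has only the survival assessment marked, with no subsequent-therapy assessment. The Synopsis list of reasons for leaving long-term follow-up includes "Subject misses 2 consecutive scheduled tumor assessments"; the matching list in Section 6.1 does not. Both lists include the sponsor closing the long-term collection period.

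**The concern.** A subject is validly at risk for a composite endpoint only while all its components can be observed. After progression and treatment status stop being collected, death is the only PFS#2 component that can still be recorded. Censoring at the last alive date nevertheless keeps the subject in the risk set, so the denominator of the hazard is too large and PFS#2 looks longer than it is.

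If the share of subjects losing progression follow-up differs between arms, which is possible in an open-label trial, the hazard ratio is biased in favour of the arm with more loss. No PFS#2 sensitivity analysis in either document would reveal this.

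**Working it through.** The plan states no numerical figure for PFS#2, so there is none to reproduce. The check is of the text, followed by an illustration.

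**Step 1: the rule against the data collected**

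| Period | Progression and therapy status | Vital status |
|---|---|---|
| Long-term follow-up | Yes, at least every 3 months | Yes |
| Survival follow-up | No | Yes |

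Within long-term follow-up one contact gives both statuses, so the last alive date and the last progression-free date nearly coincide. They separate for a subject who leaves that period without a PFS#2 event and is still contacted for survival, and for any contact that establishes vital status only. The written exits that can produce this are the sponsor closing the collection period (both lists) and two missed tumor assessments (Synopsis only).

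**Step 2: what the rule credits to one such subject**

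Assume exponential next-line PFS with a median of 6 months. The probability of progressing unseen during *t* months of survival-only contact is 1 − 2^(−t/6), ignoring death without progression.

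- t = 6: 1 − 2^(−1) = 50%
- t = 12: 1 − 2^(−2) = 75%

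For a subject still alive, the rule counts all of that time as progression-free.

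**Step 3: effect on the estimates (simulation; all inputs assumed)**

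Let P be time to progression, D time to death, A the end of progression reporting (for a share q of subjects) and C the end of follow-up.

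- Plan's rule: event at P if P ≤ min(A, C); otherwise event at D if D ≤ C; otherwise censored at C.
- Corrected rule: event at P if P ≤ min(A, C); otherwise censored at min(A, C).

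True median P is 6.0 months throughout. Settings 2 and 3 take C uniform over 3–18 months and a median of 10 months from progression to death.

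| Setting | Median, q = 10% | q = 20% | q = 30% | HR, 25% v 10% loss, true HR 1 |
|---|---|---|---|---|
| 1. Loss uniform over 0–12 months, then 6–12 months of survival contact | 6.1 | – | 6.3 | 0.96 (0.98 in a repeat) |
| 2. Loss uniform over 0–12 months | 6.2 | 6.4 | 6.6 | 0.93–0.95 |
| 3. Loss after a mean of 4 months | 6.35 | 6.74 | 7.25 | 0.90 |

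As a proportion of 6.0 months, setting 1 gives 6.1/6.0 = +2% to 6.3/6.0 = +5%. Setting 3 gives 6.35/6.0 = +6% to 7.25/6.0 = +21%. In settings 2 and 3 the corrected rule gives about 6.0 months at every q.

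With 30% versus 10% loss in setting 3, the plan's rule gives an HR of 0.87 if the greater loss is in Arm A and 1.12 if it is in Arm B. The corrected rule gives 0.99 and 0.98, which is 1.00 within simulation error. With equal loss in the two arms the HR stays near 1 under either rule (0.99 at 10% and 1.02 at 20% under the plan's rule).

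The corrected rule as simulated also censors deaths that occur after progression reporting has ended. A repeat run that kept those deaths as events, and changed the date only for living subjects, gave nearly the same medians. The distortion comes mainly from the censoring date.

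**The case against.** The strongest objection is that the affected group may be small. Table 2 schedules no imaging in long-term follow-up and phone contact is enough, so the exit for two missed tumor assessments has no schedule to act on. It may have been carried over from the post-treatment list, and Section 6.1 omits it. Survival-only follow-up is described as starting after PFS#2, and no passage explicitly sends a subject without a PFS#2 event into it. Withdrawal of consent and loss to follow-up usually end both kinds of data together.

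This narrows the group but does not empty it. Closure of the long-term collection period is listed in both places, separately from closure of survival follow-up. Overall survival needs vital status on every subject, so survival contact can continue after progression reporting stops.

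Two further objections stand. The loss rates, the imbalance between arms and the 6-month median are all assumed, and the result moves with them, as the table shows. The documents also record the date and site of progression but do not show that each negative progression check is dated, so the correction may need a CRF item. Finally, PFS#2 is exploratory and lies outside the Hochberg family.

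**Conclusion.** The concern holds. All three statements of the rule use a survival date to censor an endpoint that includes progression, nothing elsewhere offsets it, and the plan's other progression endpoints do not do this. The direction is certain for any subject with survival contact but no progression follow-up: PFS#2 is overstated.

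The size is not known from the documents. With 10–30% loss it is a rise of about 2–5% in the median under mild assumptions and up to about 21% with early loss. The hazard ratio moves materially only if loss differs between arms, for which the documents give no evidence either way.

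No type I error, confirmatory conclusion or sample size is affected. This is a minor correction, worth making because it is cheap.

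**What to change.** In Protocol 7.4.3.1, SAP 6.1.3.1 and SAP Table 7, censor living subjects without a PFS#2 event at the last contact, no later than the analysis cutoff, at which they were documented alive and without progression on the next-line therapy. If there is no such contact, censor at the start of that therapy. State how a death after progression follow-up has ended is treated. The last-known-alive rule can be kept as a sensitivity analysis.

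Align the long-term follow-up exit criteria in the Synopsis and Section 6.1. If the missed-assessment exit is kept, say which assessments it refers to, since none is scheduled in that period.

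The cost is one phrase in each of the three places. The contacts already take place at least every 3 months and already ask about progression. The sponsor should confirm that the CRF dates each progression-status check and add that item if it does not.

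A separate point in the same text: the formula in SAP 6.1.3.1 subtracts the randomization date, whereas that section's own definition and Table 7 start PFS#2 at the new therapy. It can be reconciled in the same edit.
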